#### **Laboratory Procedures/Evaluations**

- At the time of admission routine laboratory blood and urine tests are performed including complete blood count, WBC differentiation, electrolytes, creatinine, , INR, pro-BNP, troponine, HbA1c, thyroid function and etc. This data will be collected.
- Biological samples will be collected with everybody that signs the informed consent, at baseline and at 6 months follow-up.
- A peripheral blood sample (4.0mL EDTA, 2.7 mLcitrate; 4.5mL LithiumHeparine, 5.0 mL Serum tube 2.5mL PaxGene® RNA tube) will be obtained to assess for biomarkers and platelet function. A urinary sample (14 mL) will be collected to assess for biomarkers related to aortic valve stenosis or microvascular dysfunction through the use of proteomic analysis.
- Approval from the biobank has been obtained with a biobank application form (BB-GEN002-F003) filled in and signed by the PI and Biobank Manager.

#### 4. SCHEDULE OF EVENTS TABLE

Procedures	Screening	Baseline	At the time of TAVI	6-month follow-up
Assess inclusion and exclusion criteria	x			
Informed consent	x			
Enrolment	x			
Patient characteristics		x		x
Transthoracic echocardiography		x		x
Cardiac catheterization and FFRs		x		x
IMR measurements during Catheterization		x		x
Blood sampling		x		x
Urine sampling		x		x
SPECT		x		(x)
Transthoracic echocardiography		x		x
LVEDP measurement (2x)			x	
IMR and FFR measurements			x	
Adverse events		x		x
Serious adverse events		x		x

#### Timeline

Objective	First half 2020	Second half 2020	2021	2022	First half 2023	Second half 2023

Ethics approval	Red					
Patient recruitment		Red	Red	Red	Red	
Second catheterization			Red	Red	Red	Red
Analysis Secondary Objective (FFR versus RFR analysis)					Red	Red
Analysis Primary Objective (FFR changes at 6 months)						Red

## 5. FUNDING

Item	Cost per item (€)	Number needed	Total cost (€)
PaxGene tubes	11	400	4400,00
Regadenasone	140	80	11 200,00
Pressure Wire X	220	40	8 800,00
Total cost of study			24 400,00

## 6. ADVERSE EVENTS

During the course of this clinical investigation adverse events might occur. These adverse events will be determined by the investigator during the scheduled patient follow-ups. All serious adverse events must be reported within 24 hrs from acknowledgement. Other adverse events should only be reported whenever they affect one or more of the predefined endpoints of the study. These include all myocardial infarctions (any definition), stent thromboses and coronary revascularizations, even when these would not result in death, hospitalization, prolonged hospitalization or persistent disability. These adverse events must be reported on the respective Adverse Event Form.

### 6.1 Adverse events definition and classification

An adverse event (AE) is any untoward medical occurrence in a patient whether or not related to the investigated treatment. Any current condition that is recorded as a pre-existing condition either in the medical history or physical examination section, unless there is a change in nature, severity, or degree of incidence, is not an AE.

Classification of the adverse events has to be done according to the following criteria:

#### **Intensity**

Mild: patient's daily activities are not limited

Moderate: patient's daily activities are limited

Severe: patient is not able to perform daily activities

#### **Relation to Study Device**

1=not related

2=possibly related

3=probably related

4=definitely related

Relation to the study devices will be assessed by help of the following criteria: timely relation of the event to the procedure, known risks of the device and intervention, concomitant diseases, concomitant measures and medication, other possible explanations, as applicable. Additional criteria might exist depending on the study setup and adverse event. Documentation about judgement and causality assessment has to be available for review in the source data.

### **Relation to procedure**

1=not related

2=possibly related

3=probably related

4=definitely related

Relation to the procedure will be assessed by help of the following criteria: timely relation of the event to the procedure, known risk of the intervention, concomitant diseases, concomitant measures and medication, other possible explanations, as applicable. Additional criteria might exist depending on the study setup and adverse event. Documentation about judgement and causality assessment has to be available for review in the source data.

### **Seriousness of the Adverse Event**

In case any of the following criteria is applicable to the Adverse Event it classifies as SAE. The Adverse Event:

- results in death;
- is life threatening,
- requires inpatient hospitalization or prolongation of existing hospitalization,
- results in persistent or significant disability/incapacity,
- is a congenital anomaly/birth defect

This also applies to adverse events that may not be immediately life-threatening or result in death or hospitalization but may jeopardize the patient or may require intervention to prevent one of the other outcomes listed above.

The assessment of “seriousness” is independent from any relation to the investigational device.

Hospitalization is defined by a medical need for inpatient hospitalization. For procedures that are commonly performed ambulant and require inpatient hospitalization solely based on nonmedical needs (e.g. logistical reasons) this criterion could be considered not applicable by the investigator. Proper documentation of the reasons for decision is required in this case.

Events that are planned (e.g. elective surgery) and documented prior to study entry will not be recorded as (serious) adverse event. Medication received during this activity will be recorded.

## 6.2 Adverse device effects/serious adverse device effects

An adverse device effect is any untoward and unintended response to a medical device. This includes any event resulting from insufficiencies or inadequacies in the instructions for use or the deployment of the device as well as any event that is result of a user error.

An adverse device effect is classified as serious if it has resulted in any of the consequences characteristic of a serious adverse event or that might have led to any of these consequences if suitable action had not been taken or intervention had not been made or if circumstances had been less opportune.

## 6.3 Expected adverse events

As with any coronary intervention, there are possible risks and the possibility of developing complications:

Death, myocardial infarction, emergent repeat hospital intervention, bailout stenting, emergency CABG, aneurysm, pseudo aneurysm, distal embolization, air embolization, vessel spasm, fistulisation, haemorrhage, infection, restenosis of the vessel (greater than 50% obstruction), rupture of the vessel, stent migration/embolization, thrombosis (acute, subacute or late), failure to deliver the stent(s) to the intended site, occlusion, dissection, arrhythmias, prolonged angina, cardiac tamponade, perforation, hypotension, haematoma, allergic reaction, fever, stroke, renal failure, balloon rupture, dissection of non-treated site, retained pieces of dilatation catheter, stent compression, angina pectoris, bleeding complications, endocarditis, hemodynamic changes to flow, injury of the coronary artery, ischemia, palpitations, pulse arrhythmia, pyrogenic reaction, sepsis/infection, unstable angina, ventricular fibrillation.

However, the additional risk related to additional investigation-related measurements (measurement of the IMR and LVEDP), is extremely low.

## 7. WITHDRAWAL FROM STUDY/STUDY DISCONTINUATION

A patient's participation in the trial is voluntary and the patient may refuse to participate or withdraw from the trial, at any time, without penalty or loss of benefits to which the patient is otherwise entitled.

Drop outs are defined as patients:

- who decided not to continue the study/not to perform the follow-up visits for whatever reason
- who died

When a participant is withdrawn from the study, follow-up by phone call will be continued, unless the patient does not provide consent to follow-up. However, all data collected prior to discontinuation from the study will be retained in the database.

## 8. DATA COLLECTION

### 8.1 Data collection

The investigator or an individual designated by the investigator is responsible for recording all data from the study in patient's medical history and Case Report Form.

### 8.2 Protocol deviations

A protocol deviation is defined as an event where the clinical investigator or site personnel did not conduct the study according to the clinical investigation plan.

### 8.3 Record retention by study site

All study records and reports will remain in file at the study sites for a minimum of 25 years after completion of the study and will further be retained in accordance with local applicable law and guidelines.

### 8.4 Monitoring of data to source documents

A Case Report Form will be completed at the study site for each subject enrolled in the study. The case report forms will contain a record of the subject's eligibility to enter the study, medical history, pre procedure work up and clinical laboratory results, concurrent medications, plus a record of all devices used during the procedure, all procedural complications and adverse events, discharge, follow up, and any non-scheduled visit involving a late adverse event requiring hospitalization or additional procedures. The case report forms will be monitored at the site to verify source data accuracy and provide quality assurance.

## 9. STATISTICS AND ANALYSIS

### 9.1 Sample Size

The sample size for the ***primary objective*** (change in FFR after aortic valve intervention) is based on previous measurements of FFR in patients with aortic stenosis, where a standard deviation of the data was reported. An expected mean FFR of 0.82 with a standard deviation of 0.08 was used in the calculation. Fifty eight (58) patients with pre- and post-interventions catheterizations will be sufficient to detect a reduction in the FFR from 0.82 to 0.79 with an alpha level of 0.05 and power of 0.80. A total sample of 100 patients with baseline measurements of which 80 patients will undergo (T)AVR without revascularisation (20% will undergo revascularisation) and in this way are eligible for pre-and post-intervention catheterization will allow for a 25 % drop-out during the follow-up phase of the study. Missing values will predominantly be at random. Therefore, the primary endpoint will be assessed using complete case analysis. To account for missing values, the number of patients will be increased from 58 to 80 (since missing data will be excluded from analysis).

For the ***secondary objective*** (comparison of FFR versus RFR): approximately 10-20% will have left main CAD, triple vessel disease, prior myocardial infarction or tandem lesions and will not be eligible for SPECT. One Hundred patients with baseline measurements will allow a 20% drop-out to end up with 80 patients with both baseline SPECT and invasive measurements. Yamanaka *et al.* found that a sample of 80 patients was necessary to determine the optimal cutoff value of iFR for indicating myocardial ischemia. Since RFR and iFR have an extremely high correlation (0.99), the same number of patients (80) is expected to achieve an area under the ROC curve of 0.70 with 0.90% power at a significance level of 0.05 in a 2-sided test.

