Exclusion criteria	
1. The procedure is an emergency and/or the patient is unstable.
 
2. Pregnancy or lactation
 
3. Haemodynamically unstable patients
 
4. Killip class III-IV heart failure
 
5. Previous coronary artery by-pass in the artery being assessed
 
6. Contra-indications for adenosine administration: severe asthma or pre-existing type 2 AV-block
 
7. No significant coronary artery disease (<50% stenosis on angiography).
 
8. Critical coronary artery disease deemed by the Heart Team to require immediate revascularization
 
9. Patients will be excluded from the SPECT study (secondary objective) if they have a left main coronary stenosis >50%, triple vessel disease, previous myocardial infarction in the same coronary artery & tandem lesions (separated by >10mm) requiring independent evaluation in the same coronary artery since these factors interfere with the SPECT analysis.

Number of patients	
 
• 80 patients with pre- and post-intervention (TAVI or SAVR) catheterizations 
 
○ Fifty Eight t (58) patients with pre- and post-interventions catheterizations will be sufficient to detect a reduction in the FFR from 0.82 to 0.79 with an alpha level of 0.05 and power of 0.80. A total sample of 100 with baseline measurements and subsequent 80 patients who will undergo (T)AVR without revascularisation and are eligible for a pre-and post-
 
 
 

	
intervention catheterization will allow for a 25% drop-out during the follow up phase of the study.
 
 
○ This flow with patient numbers and dropout is illustrated in figure 1 for clarity.
 

Study duration	3 years (or earlier when the 80 pt's with an aortic valve procedure without revascularisation will be included)

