If TAVI/SAVR results in a significant improvement in LV remodelling and microvascular function, it should be expected that the current invasive gold-standard for measuring microvascular resistance (IMR; index of microcirculatory resistance) would improve several months after the valve intervention. If this is the case then the FFR measurement should be more accurate (as it is in patients without aortic stenosis). The question is whether a pre-TAVI/SAVR index (based on a combination of FFR and IMR) could be used in the future for assessing intermediate lesions in these patients. Developing a “corrected” FFR measurement of intermediate coronary artery lesions based on the presence or absence of microvascular dysfunction would be very useful in the pre-operative work-up of patients with aortic stenosis and would have important prognostic implications. This will be accomplished by first determining the FFR 6 months after intervention (TAVI or SAVR), when it is anticipated that the microvascular function would have returned to normal, and comparing this with the FFR prior to the intervention to determine if there is a significant change in the FFR after intervention. At the same time microvascular function will be assessed in order to develop a “corrected” FFR, which can be used in the future to determine whether or not coronary lesions need to be revascularized in patients with aortic stenosis.

The theoretical model of a serial stenosis by the AS and the coronary narrowing in our study is explained in the figure 1 in the publication of Zelis et al. It is expected that the FFR will indeed decrease after TAVI and that there will be an acute (change of intercept) and chronic (change of slope) effect of the procedure on the coronary resistance. To separate these two issues we will try to measure the FFR immediately after TAVI and 6 months after TAVI. In addition the left ventricular filling pressure/ end-diastolic pressure (LVEDP) will be measured during the TAVI procedure immediately before and after valve implantation. The measurement (the delta LVEDP) will be an important marker of the “intercept” that changes acutely. To make sure the measurements of IMR, FFR and RFR are correct these will be performed twice and an average value will be used. This will also allow us to test the reproducibility.

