### 3.6 Exclusion criteria

1. The procedure is an emergency and/or the patient is unstable.
2. Pregnancy or lactation
3. Haemodynamically unstable patients

4. Killip class III-IV
5. Previous CABG
6. Contra-indications for adenosine administration: severe asthma or pre-existing type 2 AV-block
7. No significant coronary artery disease (<50% stenosis on angiography).
8. Critical coronary artery disease deemed by the Heart Team to require revascularization.
9. Patients will be excluded from the SPECT study (secondary objective) if they have a left main coronary stenosis >50%, severe triple vessel disease, previous myocardial infarction in the same coronary artery & tandem lesions (separated by >10mm) requiring independent evaluation in the same coronary artery since these factors interfere with the SPECT analysis.

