At this time three boluses of room-temperature saline are administered in order to measure the intra-coronary flow during hyperemia by the method of thermodilution. This extra step, which is investigational, adds no additional risk or cost to the patient. However, it permits the calculation of flow and microvascular resistance or IMR (index of microvascular resistance) using Coroflow® software (Coroventis, Uppsala, Sweden). IMR is already clinically indicated in several other groups of patients (with suspected microvascular dysfunction) and is used on a routine basis in patients in our cardiac catheterization laboratory.

In order to assist the Heart Team in deliberation over the ischemic importance of intermediate coronary lesions, SPECT imaging is clinically indicated during the pre-operative/interventional work up. This will be carried out in the Department of Nuclear Medicine according to routine clinical practice under the guidance of [name]. If adenosine cannot be used then regadenoson will be used.

Intra-coronary assessment of intermediate lesions is part of routine clinical practice. The decision to revascularize and the method of revascularization (percutaneous coronary intervention versus coronary artery bypass grafting) of patients with aortic stenosis based on intra-coronary measurements and non-invasive measures of ischemia (SPECT) is discussed by the Heart Team (including the cardiologist and cardiothoracic surgeon) and forms part of routine clinical practice. In patients who do not undergo immediate revascularization, the residual CAD should be reassessed after SAVR/TAVI. Current controversy about the validity of both intra-coronary and non-invasive tests in patients with AS necessitates further evaluation (after valve intervention) since coronary lesions should not be unnecessarily treated (Class III recommendation in the ESC guidelines).

In the patients who will undergo TAVI measurements of LVEDP will be carried out during the TAVI procedure immediately before and after valve implantation. As the catheters are already present in the ventricle of the patient at this point this does not require an extra intervention

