of risk (the pressure measured by the catheter will simply be recorded for the study data). Immediately following TAVI, intracoronary hemodynamic assessment of the intermediate study lesions will be performed with measurement of FFR, RFR and IMR. For this assessment the same arterial access used during TAVI will be used. Finally, during the six-month cardiac catheterization the coronary artery disease is assessed. During this procedure additional measurements of microvascular function (IMR) will be performed. Again, FFR is routine clinical practice, given the ambiguity of earlier measurements in the presence of aortic valve stenosis, but the additional measurements of IMR will be investigatory. As discussed before the measurements will be performed in duplicate.

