### 9.2 Statistical analysis

All quantitative variables will be tested for normal distribution according to the Kolmogorov-Smirnov test. Statistical analyses will be performed via the SPSS statistical software package,

applying a significance level of  $\leq 0.05$ . Continuous variables will be expressed as mean  $\pm$  SD. Comparisons will be done with paired t-, Wilcoxon rank signed, Mann-Whitney U- or Kruskal-Wallis test when appropriate. The chi-square test will be applied for categorical variables and results will be expressed as n (%). Analysis will be performed to compare the intra-coronary measurements (FFR, RFR, IMR) prior to intervention (group 1) versus 6 months after intervention (group 2). Descriptive statistics (mean/median, standard deviation and percentiles for continuous data; percentage for categorical data) and graphical representation (boxplots, histograms and density plots) will be used to compare both groups' characteristics. Intra-coronary measurements in both groups will then be compared and tested using statistical tests (paired t-, Wilcoxon rank signed test). The correlation between FFR and RFR will be analyzed using Pearson correlation coefficient. The diagnostic performance of RFR in indicating SPECT myocardial ischemia will be evaluated using receiver operating characteristic (ROC) curve analysis.

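### The primary paired test keeps only non-revascularised patients, who are chosen partly on the baseline FFR itself; regression to the mean can add to the expected fall, and no baseline-conditional sensitivity analysis is planned

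*Combined protocol and SAP*

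**What the plan says.** - **Who enters the paired comparison.** Section 9.1 goes from 100 patients with baseline measurements to 80: "of which 80 patients will undergo (T)AVR without revascularisation (20% will undergo revascularisation) and in this way are eligible for pre-and post-intervention catheterization". From those 80 it allows 25% drop-out to reach 58 pairs.
- **How revascularisation is decided.** Section 3.8 says that the choice to revascularise, and the method, "of patients with aortic stenosis based on intra-coronary measurements and non-invasive measures of ischemia (SPECT) is discussed by the Heart Team". The Background gives FFR at or below 0.80 as the usual mark of a significant lesion.
- **The primary test.** Section 9.2 compares values before intervention with values at 6 months: "Intra-coronary measurements in both groups will then be compared and tested using statistical tests (paired t-, Wilcoxon rank signed test"). It plans no adjustment for, or conditioning on, baseline.
- **Missing data.** Section 9.1: "Missing values will predominantly be at random. Therefore, the primary endpoint will be assessed using complete case analysis".
- **Interpretation.** Under Study Objectives, primary outcome, item 1b, a significant decrease is taken to suggest that FFR/RFR is not a valid way to assess intermediate lesions in severe AS and needs more study.
- **Exclusion 8.** The synopsis has "Critical coronary artery disease deemed by the Heart Team to require immediate revascularization"; section 3.6 has "Critical coronary artery disease deemed by the Heart Team to require revascularization".

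**The concern.** The baseline FFR does two jobs: it helps decide who stays in the paired set, and it is the before value for those who stay. If low readings are removed preferentially, the retained patients' baseline mean is partly high by chance and by visit-to-visit variation. At 6 months that part is not reproduced, so the mean falls even if valve replacement does nothing.

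The direction matters. The protocol expects a fall (0.82 to 0.79) and attaches conclusion 1b to it. Selection pushes the same way, and the paired test alone cannot show how much of an observed fall it accounts for. Averaging duplicate measurements, as the Background plans, reduces error within a session but not variation between sessions six months apart.

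The missing-data sentence is a related but separate weakness. In the technical sense, missing at random allows missingness to depend on observed values such as baseline FFR. In that case a complete-case mean change can be biased in either direction, so complete-case analysis does not follow from the premise.

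**Working it through.** **Inputs from section 9.1:** mean FFR 0.82, SD 0.08, difference 0.03, alpha 0.05, power 0.80, 58 pairs, 100 reduced to 80 by revascularisation.

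**Not in the documents, so assumed:** the slope *b* of 6-month on baseline FFR (0.5 to 1.0), the 6-month SD, and how closely decisions follow FFR.

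**1. The plan's own figure.** A two-sided paired t-test with difference 0.03 and SD of change 0.08 has power 0.802 at n = 58 and 0.795 at n = 57, so 58 reproduces. For drop-out, 58/0.75 = 77.3, so 78 are needed and 80 suffice. The sample size is not in question.

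**2. How far selection raises the retained baseline mean,** taking baseline FFR as normal (0.82, 0.08):

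- P(FFR ≤ 0.80) = Φ(−0.25) = 0.401. Only 20% are expected to be revascularised, so a sharp cut at 0.80 does not fit the plan's own figures.
- *Half of those at or below 0.80 removed.* They lie on average 0.08 × φ(0.25)/0.401 = 0.077 below the overall mean. Removing half (20.1%) raises the retained mean by 0.077 × 0.201/0.799 = 0.019.
- *Lowest 20% removed (upper bound).* The rise is 0.08 × φ(0.842)/0.80 = 0.028.

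**3. Spurious change with no valve effect** = −(1 − *b*) × rise:

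| Slope *b* | Half of FFR ≤ 0.80 removed | Lowest 20% removed |
|---|---|---|
| 0.5 | −0.010 | −0.014 |
| 0.8 | −0.004 | −0.006 |
| 0.9 | −0.002 | −0.003 |
| 1.0 | 0 | 0 |

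If decisions rest on SPECT alone, the simulated paired test keeps its 5% level (0.047 to 0.053). A slope of 1.1 reverses the sign (+0.002 to +0.003).

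**4. Two-sided type I error with 58 pairs (simulation, no true change).** The first figure takes SD 0.08 at both visits; the second holds the SD of change at 0.08.

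| Slope *b* | Half of FFR ≤ 0.80 removed | Lowest 20% removed |
|---|---|---|
| 0.5 | 16% / 16% | 28% / 29% |
| 0.8 | 9% / 7% | 14% / 8% |
| 0.9 | 7% / 5% | 9% / 6% |
| 1.0 | 5% / 5% | 5% / 5% |

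Hand check at *b* = 0.8, half rule, SD 0.08 at both visits: the SD of change is 0.08 × √(2 × 0.2) = 0.0506; the standard error is 0.0506/√58 = 0.0066; the shift is 0.0039/0.0066 = 0.58 standard errors. The normal approximation gives P(Z < −1.38) + P(Z > 2.54) ≈ 0.09.

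**5. Does conditioning on baseline remove it?** A model using all 100 baselines, with FFR, RFR and a three-level SPECT result (15% not done, and an assumed correlation of 0.75 between RFR and stable FFR), left a bias of at most 0.0007 and rejection of 4.1% to 5.1%. The drivers must be complete. When RFR and SPECT also drove removal at slope 0.5, conditioning on FFR alone left +0.007, FFR with SPECT left +0.004, and all three left −0.0004.

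**The case against.** The strongest reply is that the size rests on quantities the documents do not give. A slope of 0.5 follows only if 0.08 is both the SD of FFR at each visit and the SD of its change; section 9.1 describes it as an SD of the data, which does not establish the second. At slopes of 0.8 to 0.9 under the half rule, the bias is at most 13% of 0.03 (0.004/0.03). The Heart Team also weighs SPECT, and no FFR cut-off for revascularisation is laid down. All of this stands, and it is why 0.5 is treated as an extreme and removal of the lowest 20% as an upper bound.

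It is also fair that non-revascularised patients are the natural group for re-measuring an untreated lesion, and that item 1b is worded cautiously. This supports keeping the paired test as primary. It does not show that selection is absent.

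Three stronger readings are tempting, and the documents do not support them:

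- *A significant fall would be an artefact.* The largest spurious fall found is 0.014, less than half of 0.03.
- *The two wordings of exclusion 8 show selection on FFR before enrolment.* Both concern critical disease, which is not equated with FFR at or below 0.80, and the schedule of events puts enrolment at screening and FFR at baseline. The mismatch needs reconciling but supports no estimate of bias.
- *Drop-out also biases towards a fall.* Nothing links return at 6 months to baseline FFR, so even the sign is unknown.

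**Conclusion.** The concern holds in a limited form and should be fixed. The paired set is selected partly on the baseline measurements that form the before value, the resulting bias (where present, with a slope below 1) runs with the expected result, and no planned analysis addresses it. Under the half rule the plausible size is 0.002 to 0.004, with type I error about 5% to 9%. It is 0.010 and about 16% at the extreme slope, with an upper bound of 0.014. It can also be zero. Regression to the mean can contribute to the planned 0.03 but does not account for it in any scenario examined. Confidence is moderate, because the slope and the strength of the link between FFR and decisions are assumptions.

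The step from missing at random to complete-case analysis is invalid as written, whatever the size of the revascularisation effect.

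**What to change.** Keep the paired test as primary, and before the primary analysis:

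1. Pre-specify one likelihood-based repeated-measures sensitivity analysis. Keep the baseline data of all 100 patients; treat 6-month FFR after revascularisation or drop-out as missing; include baseline FFR, RFR and SPECT (ischaemia, no ischaemia, not done).
2. State that its target is all enrolled patients, whereas the paired test describes non-revascularised completers.
3. Report baseline FFR in retained and in revascularised patients. Report any disagreement between the two analyses when interpreting item 1b.
4. Replace the complete-case sentence in section 9.1 with the assumed drivers of missingness and how each analysis handles them.
5. Reconcile exclusion 8 between the synopsis and section 3.6.

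The Background says "To separate these two issues we will try to measure the FFR immediately after TAVI and 6 months after TAVI". In TAVI patients the change from immediately after the procedure to 6 months may be reported, but descriptively only. It misses the acute effect and SAVR patients. With an assumed 29 or 44 pairs and an SD of change of 0.08, it detects about 0.041 or 0.034 at 80% power, not 0.03.

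**Cost.** SAP wording and one modest analysis of data already planned; no new procedure. The all-enrolled estimate is hypothetical for revascularised patients and extrapolates a linear relation to low FFR. Its standard error runs from about that of the paired test to roughly 10% to 16% larger. Power for a true fall of 0.03 is 70% to 83% when the SD of change is 0.08, which suits a sensitivity role. If decisions follow graded SPECT severity, the three-level code leaves a bias of +0.001 to +0.003.
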